6.2.5.2. Laboratory Data

Missing laboratory results (immunological) will not be replaced.

6.2.5.3. Daily Recording of solicited events

For studies using paper diaries which have questions in the eCRF indicating the presence or absence of solicited events, the following rules are applicable:

- Denominators for the summary of administration site (or systemic) solicited events will be calculated using the number of subjects who respond "Yes" or "No" to the question concerning the occurrence of administration site (or systemic) events.
- When a specific solicited event is marked as having not occurred following a specific study dose (i.e., SDTM CE.CEOCCUR=N for the specified post-dose period for the event in question), all daily measurements will be imputed as Grade 0.
- When a specific solicited event is marked as having occurred following a specific study dose (i.e., SDTM CE.CEOCCUR=Y for the specified post-dose period for the event in question), any missing daily recordings will be given imputed values to allow them to contribute to the 'Any' rows but not to specific grade rows of the solicited event summary tables.
- When the occurrence of a specific solicited event is not present (i.e. SDTM CE.CEOCCUR is neither Y nor N for the specified post-dose period for the event in question) but the group

of solicited events (administration site or systemic) is marked as having occurred (i.e. SDTM CE.CEOCCUR=Y), all missing daily recordings will be given imputed values to allow them to contribute to the 'Any' rows but not to specific grade rows of the solicited event summary tables.

Note while fever is a solicited systemic event, it was not included in the group of solicited events in the eCRF question, therefore will only contribute to the 'Any' and specific grade rows if it occurred.

- The following table shows how subjects contribute to each category for a specific solicited event over the Day X to Day Y post-dose period:

Solicited event category	Subjects included in the calculation of the numerator
Any	All subjects with at least one occurrence of the adverse event at grade 1, grade 2, or grade 3 between Day X and Day Y or with the adverse event marked as present and at least one missing daily recording between Day X and Day Y
At least grade 1	All subjects with at least one occurrence of the adverse event at grade 1, grade 2, or grade 3 between Day X and Day Y
At least grade 2	All subjects with at least one occurrence of the adverse event at grade 2 or grade 3 between Day X and Day Y
At least grade 3	All subjects with at least one occurrence of the adverse event at grade 3 between Day X and Day Y

6.2.5.4. Unsolicited adverse events

Missing severity, relationship with study vaccine, and outcome of unsolicited AEs will not be replaced and will appear as 'UNKNOWN' when displayed in a statistical output.

Unsolicited AE summaries will include SAEs unless specified otherwise.

As per CDISC Vaccines Therapeutic Area guide, the solicited events which continue beyond the observation period are stored in the AE domain, but they do not contribute to the summaries of unsolicited AEs.

6.2.6. Data Derivations

6.2.6.1. Age

When age at primary vaccination in ZOSTER-041, at time of enrollment in ZOSTER-073, and at first revaccination in ZOSTER-073 is to be displayed in years, it will be calculated as the number of complete calendar years between the year of birth and the date of primary vaccination/enrollment/revaccination. For example:

DOB = 10SEP1983, Date of primary vaccination = 09SEP2018 -> Age = 34 years

DOB = 10SEP1983, Date of primary vaccination = 10SEP2018 -> Age = 35 years

In case of partial dates, the rules in Section 6.2.5.1 will be followed.

6.2.6.2. Vital signs

- Weight will be presented in kilograms. Weights reported in pounds will be converted as follows:
Weight in kilograms = Weight in pounds / 2.2

The results will be rounded to 1 decimal digit.

- Temperature ranges for fever are as follows:
 - Grade 0: <38.0 C
 - Grade 1: $\geq 38.0 - \leq 38.5$
 - Grade 2: $> 38.5 - \leq 39.0$
 - Grade 3: > 39.0

6.2.6.3. Numerical serology results

Numerical serology results will be derived from the content of IS.ISORRES in the SDTM dataset. For assays with a specific cut-off and a specific upper limit of quantification (ULOQ), the following derivation rules apply:

IS.ISORRES	Derived value
“NEG”, “-”, or “(-)”	cut-off/2
“POS”, “+”, or “(+)”	cut-off
“< value” and value is \leq assay cut-off	cut-off/2
“< value” and value is $>$ assay cut-off	value
“> value” and value is $<$ assay cut-off	cut-off/2
“> value” and value is \geq assay cut-off	value
“value” and value is $<$ cut-off	cut-off/2
“value” and value is \geq cut-off and value is \leq ULOQ	value
“value” and value is $>$ ULOQ	ULOQ
All other cases	missing

6.2.6.4. Cellular-mediated immune response

- For the descriptive analyses, the frequency of CD4 [2+] T-cells upon in vitro stimulation with the gE (induction condition) is calculated by dividing the number of activated CD4 [2+] T-cells (numerator) over the total number of CD4 T-cells involved (denominator).

$$Freq_{Induction}^{CD4[2+]} = \frac{n_{Induction}^{2+}}{N_{Induction}^{CD4}}$$

$n_{Induction}^{2+}$ = number of CD4 T cells secreting at least 2 activation markers after induction with the antigen

N^{CD4} = Total number of CD4 T cells involved in the assay (induction)

- The frequency of **gE-specific** CD4⁺ T-cells (*Spec-CD4[2+]*) for each individual subject is calculated as the difference between the frequency of CD4[2+], upon in vitro stimulation with the gE-antigen (induction condition) minus the frequency of (CD4[2+] upon in vitro stimulation in medium only (background condition). The differences less or equal to one (1) are imputed to 1 gE-specific activation marker expressing CD4[2+] T-cell per 10⁶ CD4⁺ T-cells.

$$Freq_{Specific}^{CD4[2+]} = \frac{n_{Induction}^{2+}}{N_{Induction}^{CD4}} - \frac{n_{Background}^{2+}}{N_{Background}^{CD4}} \quad \text{if } \frac{n_{Induction}^{2+}}{N_{Induction}^{CD4}} > 1 + \frac{n_{Background}^{2+}}{N_{Background}^{CD4}}$$

$$Freq_{Specific}^{CD4[2+]} = 1 \quad \text{if } \frac{n_{Induction}^{2+}}{N_{Induction}^{CD4}} \leq 1 + \frac{n_{Background}^{2+}}{N_{Background}^{CD4}}$$

$n_{Induction}^{2+}$ = number of CD4 T - cells secreting at least 2 activation markers after induction with the gE - antigen

$n_{Background}^{2+}$ = number of CD4 T - cells secreting at least 2 activation markers in the medium conditions

N^{CD4} = Total number of CD4 T - cells involved in the assay (induction of background)

- The Geometric Mean (GM) frequency calculations are performed by taking the anti-log of the mean of the log frequency transformations.
- The CMI vaccine response to gE will be based on the gE-specific data as computed above. The lower limit of linearity (LLL) for the assay (354 positive events/10⁶ CD4+ T-cells) will be used as threshold for vaccine response assessment. The vaccine response is defined as the percentage of subjects who have at least a:
 - 2-fold increase as compared to the LLL, for subjects with pre-vaccination gE-specific CD4[2+] T cell frequencies below the LLL.
 - 2-fold increase as compared to pre-vaccination gE-specific CD4[2+] T cell frequencies, for subjects with pre-vaccination gE-specific CD4[2+] T cell frequencies above the LLL.

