12.2. Appendix 2: Clinical laboratory tests

12.2.1. Clinical laboratory tests

Specific antibody (anti-gE) measurements

Anti-gE ELISA: Anti-gE Ab concentrations will be measured using an anti-gE ELISA. Diluted blood serum samples of study subjects will be added to microtiter wells pre-coated with VZV gE recombinant antigen. Secondary peroxidase-conjugated anti-human antibodies will be added, which bind to the primary human anti-gE antibodies. After incubation of the microtiter wells with a chromogen substrate solution, the enzymatic reaction will be stopped. Optical densities will be recorded and anti-gE antibody concentrations are calculated from a standard curve. The assay will be performed on human serum at GSK laboratory or another laboratory designated by GSK.

Intracellular cytokine staining

CMI responses will be performed by GSK (or designated laboratory) on thawed PBMCs by ICS. The assay will be performed on samples collected during the course of the study. This assay provides information on the frequency of CD4+ T-cells responding to culture medium or antigens (gE peptide pool) by secreting cytokine molecules involved in immunity such as IFN- γ , IL-2, TNF- α , and CD40L.

Briefly, PBMC collected from the subjects are stimulated for two hours using culture medium (for evaluation of the non-specific response), a pool of overlapping peptides covering the entire sequence of the vaccine antigen gE. Then, an intracellular block (brefeldin A) is added to inhibit cytokine secretion for a subsequent overnight incubation. Cells are then harvested, stained for surface markers (CD3, CD4 and CD8) and fixed. The fixed cells are then permeabilized and stained with anti-cytokine antibodies, washed and analyzed by cytofluorometry.

The results of ICS assays are expressed as the frequency of specific CD4+ T-cells per million total CD4+ T-cells.

PCR Assay for confirmation of suspected cases of HZ

HZ cases will be confirmed by a PCR based algorithm that assesses the presence of VZV DNA in samples, and the adequacy of the samples (by assessing the presence of β -actin DNA).

VZV and β -actin DNA in HZ clinical specimens will be assessed using real-time PCR detection by the 5' nuclease assay based on the Taqman probe technology. If the VZV PCR is negative, β -actin PCR will be performed to assess adequacy of the sample and if a specimen is found to be VZV-PCR negative and β -actin-PCR negative, it is considered to be inadequate.

CONFIDENTIAL

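### The CMI frequency equations in SAP 6.2.6.4 omit the ×10⁶ scaling, so the printed condition for keeping a background-subtracted value can never be met

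*SAP*

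**What the plan says.** SAP 6.2.6.4 derives the cell-mediated response in three steps.

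- **Frequency.** The frequency after gE stimulation "is calculated by dividing the number of activated CD4 [2+] T-cells (numerator) over the total number of CD4 T-cells involved (denominator"). The displayed formula is n/N. Neither it nor the symbol definitions contain a multiplier.
- **Background subtraction with a floor.** The gE-specific frequency is the induction frequency minus the medium-only frequency. The prose then adds: "The differences less or equal to one (1) are imputed to 1 gE-specific activation marker expressing CD4[2+] T-cell per 10⁶" CD4+ T-cells. Two displayed equations put this into symbols. The difference is kept if n/N (induction) > 1 + n/N (background); otherwise the value is 1.
- **Vaccine response.** "The lower limit of linearity (LLL) for the assay (354 positive events/10⁶ CD4+ T-cells) will be used as threshold" for response. Subjects below that limit before vaccination need a "2-fold increase as compared to the LLL"; those above it need a doubling of their own pre-vaccination value.

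Protocol 12.2.1 gives the assay's reporting unit: "The results of ICS assays are expressed as the frequency of specific CD4+ T-cells per million total CD4+ T-cells".

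**The concern.** The equations combine two scales. The frequencies are plain ratios, but the constant 1 they are compared with, and replaced by, is a count per million. As printed, the keep branch is unreachable and the replacement branch always applies.

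This section is the SAP's operative derivation of the gE-specific CD4[2+] frequency. It feeds the secondary CMI summaries in SAP 4.3.1.2.1 (long-term follow-up), 4.3.1.2.2 (revaccination active phase) and 4.3.1.2.3 (revaccination follow-up): frequencies, fold increases and response rates. The last of these sections refers back to 6.2.6.4 for the response definition. A derivation appendix should be programmable without the reader having to supply a missing constant.

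**Working it through.** The plan gives no computed figure to reproduce here. The check takes the rule as printed, then the same rule on the per-million scale.

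**Inputs from the documents.** Frequency = n/N; keep condition n/N (induction) > 1 + n/N (background); replacement value 1, described in prose as per 10⁶; lower limit of linearity 354 per 10⁶; response factor 2 (all SAP 6.2.6.4). Reporting unit per million (Protocol 12.2.1).

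**Assumed for illustration only.** N = 200,000 CD4+ T-cells in each condition and 20 positive background cells. The documents give neither figure.

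**Step 1: the printed condition.** The n cells are a subset of the N cells, so n/N (induction) ≤ 1. Background n/N ≥ 0, so 1 + n/N (background) ≥ 1. The left side can never strictly exceed the right. For example, with 2,000 per million induced and 100 per million background, the test is 0.002 > 1.0001, which is false, although the difference is 1,900 per million. An exact-fraction enumeration over every n ≤ N, with N from 1 to 20 in each condition, covers 230 × 230 = 52,900 cases; the condition held in 0.

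**Step 2: both scales compared.** Background is 20/200,000 = 0.0001, or 100 per 10⁶.

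| Induced positive cells | Difference per 10⁶ | Rule as printed | Rule with ×10⁶ |
|---|---|---|---|
| 20 | 0 | 1 | 1 (floor) |
| 30 | 50 | 1 | 50 |
| 91 | 355 | 1 | 355 |
| 162 | 710 | 1 | 710 |
| 500 | 2,400 | 1 | 2,400 |
| 2,000 | 9,900 | 1 | 9,900 |

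For example, (162 − 20)/200,000 × 10⁶ = 710.

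**Step 3: effect on vaccine response.** A subject below the limit before vaccination must reach 2 × 354 = 708 per 10⁶.

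- Printed rule, the 1 read as 1 per 10⁶: every pre- and post-vaccination value is 1, every fold increase is 1/1 = 1, and 1 < 708, so the response rate is 0%.
- Printed rule, the 1 read as a proportion and rescaled afterwards: every value is 1,000,000 per 10⁶. All subjects are then above the limit before vaccination and would need 2,000,000, so the response rate is again 0%.
- Scaled rule: only differences of at most 1 per 10⁶ are replaced, and 708 is attainable (the 162-cell row gives 710).

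**The case against.** The strongest reply is that the plan already states the scale. The sentence introducing the equations gives the replacement value per 10⁶, the lower limit of linearity is per 10⁶, and Protocol 12.2.1 reports the assay per million. No section says the frequency is to be analysed as a 0–1 proportion. On the stated scale the 1 is one cell per million and the rule is an ordinary floor. A literal program would also expose itself: every subject would have the same value at every visit, and the planned means, SDs, quartiles and graphs would show it at once.

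Most of this stands. A reader might infer from the equations that the planned CMI analysis will collapse, with all values imputed and a 0% response rate. The documents do not support that inference. It requires reading the equations apart from the sentence they illustrate and from every other place where a unit is given.

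The reply does not rescue the equations. The prose definition of the frequency omits the factor as well, so nothing suggests that a symbol was lost from the display. The wording that triggers the imputation, a difference of one or less, has no unit of its own; the unit appears only on the replacement value. The equations should settle the question, and they settle it the wrong way.

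**Conclusion.** Wrong as written: a formula and unit error in the derivation of the secondary CMI endpoints, with recoverable intent. That the printed condition is impossible follows from algebra and needs no assumption. That the per-million scale is intended rests on the three places that state it, all of which agree. The consequences for fold increase and response rate arise only if the equations are coded literally, and should not be taken as the plan's expected results. The cell counts in the table are illustrative and the conclusion does not depend on them. The point concerns the CMI sub-cohort only (up to 40 subjects). Sample size, response threshold, analysis sets and primary endpoints do not change.

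**What to change.** Three edits to SAP 6.2.6.4:

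1. Define Freq = 10⁶ × n/N for both the induction and the background condition.
2. Use these scaled quantities in both branches: keep Freq(induction) − Freq(background) if Freq(induction) > 1 + Freq(background); otherwise set the value to 1.
3. Put the unit on both halves of the imputation sentence: differences ≤ 1 per 10⁶ CD4+ T-cells are set to 1 per 10⁶. Rescaling the formulas alone would leave the trigger without a unit.

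It is also worth confirming that the analysis program already works per million. The cost is a short text correction; data collection, design and thresholds stay as they are.

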6.2.6.5. Onset day

The onset day for an event (e.g., AE, concomitant medication/vaccination) is the number of days between the last study dose and the start date of the event. This is 1 for an event occurring on the same day as a study dose (and reported as starting after study dose).

6.2.6.6. Duration of events

The duration of an event with a start and end date will be the difference between the start and end date plus one day, i.e., an event that starts on 3 March 2018 and ends on 12 March 2018 has a duration of 10 days. Duration is 1 day for an event starting and ending on the same day.

The duration of solicited events will be calculated as the sum of the individual days with the AE reported at grade 1 or higher during the solicited event period.

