Secondary	
 Percentage of subjects with at least one local AE (solicited and unsolicited), with at least one general AE (solicited and unsolicited), and with any AEs during the solicited 7-day follow-up period will be tabulated with exact 95% CI after each revaccination dose and overall. The same computations will be done for Grade 3 AEs. Percentage of subjects reporting each individual solicited local AE (any grade and Grade 3) and solicited general AE (any grade, Grade 3, any related and Grade 3 related) during the 7-day follow-up period (i.e., on the day of revaccination and 6 subsequent days) will be tabulated after each revaccination dose and overall. Duration of solicited local and general AEs within 7 days and entire duration will be tabulated overall. Percentage of subjects with any unsolicited AEs during the 30-day follow-up period (i.e., on the day of revaccination and 29 subsequent days) with its exact 95% CI will be tabulated by Medical Dictionary for Regulatory Activities (MedDRA) preferred term. Similar tabulation will be done for Grade 3 unsolicited AEs, for any causally related unsolicited AEs, for Grade 3 causally related unsolicited AEs, for Grade 3 non-serious unsolicited AEs, for Grade 3 causally related non-serious unsolicited AEs and for unsolicited AEs resulting in a medically attended visit. Percentage of subjects with at least one report of SAE classified by the MedDRA SOC and PTs and reported from revaccination Dose 1 up to 30 days and 12 months post- last revaccination dose will be tabulated with exact 95% CI. SAEs will be also described in detail. Percentage of subjects with at least one report of causally related-SAE classified by the MedDRA SOC and Preferred Terms and reported from revaccination Dose 1 up to 30 days and 12 months post-last revaccination dose, and up to study end (Month 49) will be tabulated with exact 95% CI. Related-SAE will be also described in detail. Percentage of subjects with at least one pIMD classified by the MedDRA SOC and Preferred Terms and percentage of subjects with at least one pIMD with causal relationship, reported from Dose 1 up to 30 days and 12 months post- last revaccination dose will be tabulated with exact 95% CI. Percentage of subjects with at least one biopsy-proven allograft rejection and causal relationship reported from Dose 1 up to study end (Month 49) will be tabulated with exact 95% CI. Percentage of subjects reporting unsolicited AEs resulting in a medically attended visit from Dose 1 up to 30 days post-last revaccination dose will also be tabulated with exact 95% CI. Fatal SAEs will be described by onset date of SAE and date of death SAEs (including fatal SAEs), pIMDs and withdrawal due to AE(s) will be described in detail. Listing of withdrawals due to AE and SAEs will be provided Listing of subjects with confirmed HZ episode will be provided. Listing of subjects with biopsy-proven allograft rejection will be provided.

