Revaccination active and follow-up phases - Safety assessment 
 To evaluate reactogenicity and safety of the HZ/su vaccine after each revaccination. 	
In all revaccinated subjects:
 
 Solicited local and general AEs: 
 Occurrence, duration, and intensity of solicited local AEs within 7 days after each revaccination (i.e., the day of revaccination and 6 subsequent days); Occurrence, duration, and intensity of solicited general AEs within 7 days after each revaccination dose (i.e., the day of revaccination and 6 subsequent days) and causal relationship to revaccination by investigator assessment. Unsolicited AEs

Objectives	Endpoints

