4.3.2.2. Revaccination phase

The results for the analysis of safety in the revaccination phase will be tabulated as follows:

- Number and percentage of subjects with at least one local AE (solicited and unsolicited), with at least one general AE (solicited and unsolicited), and with any AEs during the solicited 7-day follow-up period will be tabulated with exact 95% CI after each revaccination dose and overall. The same computations will be done for Grade 3 AEs and medically attended AEs. Number and percentage of subjects reporting each individual solicited local AE (any grade and Grade 3) and solicited general AE (any grade, Grade 3, any related and Grade 3 related) during the 7-day follow-up period (i.e., on the day of

[figure not shown]
revaccination and 6 subsequent days) will be tabulated after each revaccination dose and overall.

- Duration of solicited local and solicited general AEs within 7 days and entire duration (lasting longer than 7 days) will be tabulated descriptively overall.
- Number and percentage of subjects with any unsolicited AEs during the 30-day follow-up period (i.e., on the day of revaccination and 29 subsequent days) with its exact 95% CI will be tabulated by MedDRA Primary SOC and PT. Similar tabulations will be done for Grade 3 unsolicited AEs, for any causally related unsolicited AEs, for Grade 3 causally related unsolicited AEs, for Grade 3 non-serious unsolicited AEs, for Grade 3 causally related non-serious unsolicited AEs, non-serious unsolicited AEs, non-serious causally related unsolicited AEs, and for unsolicited AEs resulting in a medically attended visit.
 - The number and percentage doses followed by unsolicited AEs during the 30-day follow-up period with its exact 95% CI will also be tabulated.
- Number and percentage of subjects with at least one report of SAE classified by MedDRA Primary SOC and PT and reported from revaccination Dose 1 up to 30 days post-last revaccination dose, from revaccination Dose 1 up to 12 months post- last revaccination dose, and from revaccination Dose 1 up to study end will be tabulated with exact 95% CI.
- Number and percentage of subjects with at least one report of causally related-SAE classified by MedDRA Primary SOC and PT and reported from revaccination Dose 1 up to 30 days post-last revaccination dose, from revaccination Dose 1 up to 12 months post-last revaccination dose, and from revaccination Dose 1 up to study end will be tabulated with exact 95% CI.

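### The SAP's day-count rule for solicited reactions caps the promised entire-duration tabulation at 7 days per dose

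*SAP*

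**What the plan says.** Both documents promise two duration outputs for solicited events. Protocol 10.3.4 states: "Duration of solicited local and general AEs within 7 days and entire duration will be tabulated overall". SAP 4.3.2.2 repeats this and adds a gloss: "Duration of solicited local and solicited general AEs within 7 days and entire duration (lasting longer than 7 days) will be tabulated descriptively overall".

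SAP 6.2.6.6 contains two duration rules. The general one reads "The duration of an event with a start and end date will be the difference between the start and end date plus one day", with the illustration that "an event that starts on 3 March 2018 and ends on 12 March 2018 has a duration of 10 days". The one written for solicited events, with no restriction to either output, is that duration is "calculated as the sum of the individual days with the AE reported at grade 1 or higher during the solicited event period". SAP 1.1 sets the solicited period for the endpoint as "within 7 days after each revaccination (i.e., the day of revaccination and 6 subsequent days", which makes 7 days per dose.

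SAP 6.2.5.4 deals with reactions that outlast the period: "solicited events which continue beyond the observation period are stored in the AE domain, but they do not contribute to the summaries of unsolicited AEs".

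**The concern.** The entire-duration output exists to show reactions that run past the solicited period. A rule that counts only days inside that period cannot show them. If the programmer applies the rule specific to solicited events, which is the natural choice, both duration outputs come from the same count.

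The report could then show an entire-duration summary with a maximum of 7 days. A reader would take that as evidence that no reaction lasted longer, when the derivation allows no other result. Reactogenicity after each revaccination is a stated secondary objective, and the study is small (68 subjects enrolled, SAP 1.2). A few prolonged reactions would therefore be visible if they were summarised correctly.

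The days after Day 7 are not picked up in the other reaction summaries. Continuing solicited events are excluded from the unsolicited AE summaries, and the combined solicited and unsolicited tabulation in SAP 4.3.2.2 covers the same 7 days. SAP 4.8, which lists departures from the protocol's analyses, does not say that entire duration was dropped.

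**Working it through.** **Inputs.** The solicited period is Days 1 to 7, with Day 1 the day of revaccination (SAP 1.1). The two rules come from SAP 6.2.6.6. Take a reaction that is continuously at grade 1 or higher from onset day a (1 to 7) to last day b.

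- General rule, calendar span: S = b − a + 1
- Solicited rule, days counted inside the period: C = min(b, 7) − a + 1

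**The plan's own example.** For 3 to 12 March, S = 12 − 3 + 1 = 10 days. This reproduces the SAP's figure.

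**The cap.** C is largest when a = 1 and b is 7 or later: C = 7 − 1 + 1 = 7. No end date can raise it.

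**The two rules side by side.**

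| Reaction | Solicited rule C | Span S | Days not counted |
|---|---|---|---|
| Day 1 to Day 7 | 7 | 7 | 0 |
| Day 1 to Day 10 | 7 | 10 | 3 |
| Day 2 to Day 12 | 6 | 11 | 5 |
| Day 5 to Day 14 | 3 | 10 | 7 |
| Day 1 to Day 30 | 7 | 30 | 23 |

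**A 10-day reaction by onset day.** Here b = a + 9, which is always beyond Day 7, so C = 7 − a + 1 = 8 − a. For onset on Days 1, 2, 3, 4, 5, 6 and 7 the score is 7, 6, 5, 4, 3, 2 and 1 days. The same 10-day reaction is shortened more the later it starts.

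**Consequence.** Under the solicited rule the within-7-days value and the entire-duration value are the same number for every event, and the SAP's gloss of lasting longer than 7 days can never be met.

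**The case against.** The best defence is that SAP 6.2.6.6 has two rules and the SAP can be read so that each has its place. The day count would serve the 7-day output. The start-and-end-date rule would serve continuing events, which SAP 6.2.5.4 holds in the AE domain and for which SAP 6.2.5.1 has date imputation rules. On that reading nothing is capped. The reading is possible, but no sentence assigns the general rule to the entire-duration output, and the rule naming solicited events is the more specific one. The defence shows that the repair is easy. It does not show that the text is adequate.

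Other parts of the defence stand, and they limit the point. A reader might infer that the prolonged part of a reaction is lost or appears nowhere. The documents do not support that: an entire-duration tabulation is named, the continuing events are stored, and a reaction that became serious would appear in the SAE outputs. Keeping continuing events out of the unsolicited summaries also has a sensible purpose, since they are already counted as solicited.

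A reader might also infer that a named secondary endpoint goes undelivered. The endpoint is worded as duration within 7 days, and the day count delivers that. Nor do the documents make prolonged reactions the leading safety question. The vaccine risks listed in protocol 3.3.1 are hypersensitivity, immune-mediated disease and allograft rejection, and injection-site reactions are described there as short-lived.

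Finally, a calendar span is not the same measure as a count of symptomatic days. A reaction on Days 1 and 5 only is 2 days by the count and 5 − 1 + 1 = 5 days by the span. Some events may also have no end date: protocol 12.5.12.1.1 reviews unresolved AEs only until 30 days after the last vaccination, and SAP 6.2.5.1 imputes partial dates, not absent ones. The fix has to deal with both.

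**Conclusion.** The point holds as a conflict between a promised output and the rule written to derive it. Applied as written, SAP 6.2.6.6 limits the entire-duration output to 7 days per dose and makes it identical to the within-7-days output.

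The cap follows from the text alone and needs no assumption about how long reactions last. How many events it would shorten, and by how much on average, cannot be derived, because neither document gives a distribution of durations. The worked cases assume a reaction present on every day from onset to end.

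The consequence is limited to a descriptive tabulation in a single-group study. The 7-day secondary endpoint, the primary immunogenicity endpoints and the sample size are unaffected. It is still worth correcting before the final analysis, because the output as specified could be mistaken for a finding that no reaction was prolonged.

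**What to change.** Amend SAP 6.2.6.6 as follows.

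1. Restrict the day-count rule to the within-7-days output.
2. For the entire-duration output, use end date minus start date plus 1, taking the end date of a continuing event from its AE-domain record.
3. State that this is a calendar span and may include symptom-free days.
4. Report events with no end date as ongoing, censored at last follow-up, and give their number. Partial end dates can follow SAP 6.2.5.1.

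The cost is a few sentences and one extra derivation. The SAP says the continuing events are already stored, but how their end dates are collected should be confirmed. The small downside is that the two duration outputs will be on slightly different scales for intermittent reactions, which a table footnote can explain.
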